4.4.2 Treatment-related Discomfort

After each laser treatment, subjects will be asked to rate the average amount of discomfort experienced during treatment and immediately after laser treatment.

4.4.3 Phone Follow-up

Phone follow-up will be conducted for all subjects by the Investigator's staff at 3 days after each laser treatment. Data recorded on the phone follow-up questionnaire will be evaluated for adverse events, event duration and adverse event resolution. The Phone Follow-up Questionnaire is presented in **Appendix 5**.

4.5 Photographs

Standardized digital photographs will be taken of each subject's treatment area at baseline, prior to all laser treatments and at each follow-up. Any jewelry will be removed from the area being photographed. For facial photographs, hair will be pulled away from the face with a headband and subject will have recently cleansed skin. Photographs will be taken prior to all laser treatments and at each follow-up visit. Facial photographs will be obtained from 3 angles: with the subject facing forward, 90° to the right and 90° to the left. Photographs will be taken in the same windowless room equipped with adequate lighting. The room lighting, camera positioning and subject positioning should be consistent for all study visit photographs. Digital camera settings should remain the same for all photographs and the highest resolution settings should be utilized.

4.6 Study Discontinuation

Cutera, Inc. (the sponsor) has the right to terminate this study at any time. Reasons for terminating the study may include, but are not limited to, the following: incidence or severity of adverse events in this or other studies indicates a potential health hazard to subjects; subject enrollment is unsatisfactory; number of protocol deviations is unacceptable; data recording is inaccurate or incomplete; or questionable study site compliance with ICH-E6, Good Clinical Practice.

4.7 Investigator Selection

The Investigator will be invited to participate in the study based on his or her medical specialty, experience conducting clinical research studies and experience in the use of light-based devices for aesthetic indications. Access to potential study subjects and the Investigator's sincere interest in this study along with expressed willingness to cooperate with the study process and requirements was also considered.

5 Study Population

5.1 Study Subject Recruitment and Selection

Up to 20 male or female subjects, ages 18 to 75, with Fitzpatrick Skin Type I-VI who desire laser treatment for skin rejuvenation on the face. Subjects will be recruited to participate from the local population. Subjects may also be recruited from the Investigator's existing patient database or from patients who

present themselves to the study site requesting treatment. Only subjects who meet all eligibility criteria and who provide written informed consent will be enrolled into the study.

Each subject will be evaluated by the Investigator to assess his/her suitability for entry into the study according to the following inclusion and exclusion criteria.

5.1.1 Inclusion Criteria

To be included in the study, subjects must meet all of the following Inclusion Criteria:

1.	Female or Male, 18 to 75 years of age (inclusive).
2.	Fitzpatrick Skin Type I – VI (Appendix 2).
3.	Desires photo-rejuvenation of the skin or improvement in the appearance of acne scarring.
4.	Subject has visible signs of acne scarring or moderate sun-damaged and/or aging skin in the treatment area with visible areas acne lesions and scars, fine rhytides, lentigines or pigmentation, diffused redness erythema and skin texture
5.	Subject must be able to read, understand and sign the Informed Consent Form.
6.	Must be willing and able to adhere to the treatment and follow-up schedule and post-treatment care instructions.
7.	Willing to have very limited sun exposure and use an approved sunscreen of SPF 50 or higher on the treatment area every day for the duration of the study, including the follow-up period.
8.	Willing to have digital photographs taken of the treatment area and agree to use of photographs for presentation, educational or marketing purposes.
9.	Agree to not undergo any other procedure(s), including injectable agents, for skin rejuvenation during the study and has no intention of having such procedures performed during the course of the study.
10.	Post-menopausal or surgically sterilized, or using a medically acceptable form of birth control at least 3 months prior to enrollment and during the entire course of the study, and no plans to become pregnant.

5.1.2 Exclusion Criteria

Subjects will be excluded from the study if they meet any of the following Exclusion Criteria:

1.	Participation in a clinical trial of another drug, or device administered to the target area, during the study.
2.	Any type of prior cosmetic treatment to the target area within 6 months of study participation, such as laser or light-based procedures or surgery.
3.	Prior injection of botulinum toxin, collagen, hyaluronic acid filler or other dermal filler within 6 months of study participation.
4.	History of malignant tumors in the target area.
5.	Skin abnormalities in the target area, e.g., cuts, scrapes, wounds, large moles.
6.	Pregnant and/or breastfeeding.
7.	Having an infection, dermatitis or a rash in the treatment area.
8.	Significant concurrent illness, such as diabetes mellitus or cardiovascular disease, e.g., uncontrolled hypertension.

9.	History of keloid scarring, hypertrophic scarring or of abnormal wound healing.
10.	History of immunosuppression/immune deficiency disorders or currently using immunosuppressive medications per investigator's discretion.
11.	History of vitiligo, eczema, or psoriasis.
12.	History of connective tissue disease, such as systemic lupus erythematosus or scleroderma.
13.	History of seizure disorders due to light.
14.	Any use of medication that is known to increase sensitivity to light according to Investigator's discretion.
15.	History of disease stimulated by heat, such as recurrent herpes simplex and/or herpes zoster (shingles) in the treatment area, unless treatment is conducted following a prophylactic regimen
16.	History of pigmentary disorders, particularly tendency for hyper- or hypo-pigmentation.
17.	Systemic use of retinoid, such as isotretinoin, as applicable, within 6 months of study participation.
18.	Topical use of retinoid, such as isotretinoin, as applicable, on the treatment area within 1 month of participation.
19.	Anytime in life, having have used gold therapy (gold salts) for disorders such as rheumatologic disease or lupus.
20.	Excessively tanned in areas to be treated or unable/unlikely to refrain from tanning during the study.
21.	Current smoker or history of smoking within 6 months of study participation.
22.	As per the Investigator's discretion, any physical or mental condition which might make it unsafe for the subject to participate in this study.

5.2 Subject Numbering

[figure not shown]
If a subject meets the study eligibility criteria and is willing to participate, the subject will be assigned a study subject identification number. This number is comprised of a sequential subject number and the subject initials (first and last names).

[figure not shown]
[figure not shown]
[figure not shown]
5.3 Subject Discontinuation Criteria

[figure not shown]
If possible, every subject should remain in the study until completion of the required follow-up period. However, participation in this study is completely voluntary and a subject can choose to withdraw from the study at any time. Decision to withdraw will not affect or prejudice the subject's continued medical care in any way. In those instances, the investigator will attempt to obtain a final clinical assessment and an adverse device effect evaluation for the subject prior to this withdrawal. A subject will be considered lost to follow-up only after three unsuccessful, documented attempts to contact the subject have been made.

In addition, a subject can be discontinued for any of the following reasons: the Principal Investigator decides that continuing in the study would not be in the subject's best interest, a subject is noncompliant with the protocol, a subject has a serious reaction to the treatment, a subject develops any of the exclusion criteria during the study period or the study is stopped by the study sponsor.

6

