7.2 Recording ADEs and SADEs

All ADEs/SADEs will be: (1) evaluated and must be recorded in the subject's medical chart and in the study case report forms (CRFs); (2) monitored and tracked from the time of the first treatment with the Cutera Enlighten laser system.

At each contact with the subject, the investigator must seek information on ADEs/SADEs by specific questioning and, as appropriate, by examination. ADEs/SADEs may be observed by the investigator and/or clinical research staff, elicited from the subject and/or family member or volunteered by the subject. All observed and volunteered adverse signs and symptoms, anticipated or unanticipated, regardless of severity or frequency, will be recorded in the case histories (medical chart and CRFs). Included in the description should be the nature of the sign or symptom, the date of onset, date of resolution (duration), the severity, anticipated or unanticipated, the relationship to study treatment or other therapy, the action taken (if any), and the outcome.

All SADEs, anticipated or unanticipated, must be reported to Cutera immediately but not later than 5 working days. The SADE must be recorded in: (1) the AE CRF and (2) a written report must be submitted to Cutera within five (5) working days after the investigator first learns of the event and is to include a full description of the event and sequelae, in the format detailed by the Cutera Serious Adverse Device Effect Form.

7.3 Follow-up of Subjects after ADEs and SADEs:

All reported ADEs/SADEs should be followed until resolution or until the subject's participation in the study ends. Resolutions of ADEs/SADEs are to be documented on the appropriate CRFs. All ADEs that result in permanent discontinuation from this clinical trial, whether serious or not, should also be reported on the subject Non-Completion of Study Form.

8 Potential Risks / Benefits

8.1

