10.3.1.2 Safety Analyses

The safety variables for this study are:

- Incidence and severity of adverse effects during study duration (to be displayed descriptively as counts and frequency distributions)
- Subject discomfort (pain) during treatment (to be descriptively displayed).

Enrolled subjects who received at least one treatment will be included in the safety analyses. Device-related and procedure-related adverse effects (AEs) and subjects who prematurely terminate from the study due to an adverse device effect, including the treatment-related pain ratings, as reported on case report forms will be tabulated and analyzed. For a given AE term, counting will be done by subject, not by event, i.e. for a subject reporting the same AE more than once, the event will be counted only once, at the most severe and most-related occurrence. The number and percentage of subjects experiencing each AE Term will be descriptively summarized. Statistical hypothesis testing will not be performed for safety data.

Interim analyses of adverse events and adverse device effect incidence and severity will be performed when all treated subjects have completed the 12 week post-final treatment visit. At the conclusion of the study, complete analyses of the safety variables will be displayed descriptively.

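### On the printed wording of 5.3 and 7.3, an adverse device effect that leads to a subject's discontinuation can go unfollowed while still unresolved

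*Combined protocol and SAP*

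**What the plan says.** Section 5.3 (Subject Discontinuation Criteria) opens with retention as the aim: subjects should stay, where possible, until follow-up is complete. It then covers voluntary withdrawal, where the investigator will try to obtain a last clinical and ADE evaluation. A separate paragraph lists reasons for which a subject can be discontinued, including "a subject has a serious reaction to the treatment, a subject develops any of the exclusion criteria during the study period".

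Section 7.2 sets out how ADEs and serious ADEs (SADEs) are found and recorded:

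- On ascertainment: "At each contact with the subject, the investigator must seek information on ADEs/SADEs by specific questioning and, as appropriate, by examination".
- The description of each event is to contain, among other items, "the date of onset, date of resolution (duration), the severity, anticipated or unanticipated", and also the outcome.
- A SADE needs a written report to the sponsor within 5 working days, which "is to include a full description of the event and sequelae".

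Section 7.3 sets the end of follow-up: "All reported ADEs/SADEs should be followed until resolution or until the subject's participation in the study ends". For ADEs that lead to permanent discontinuation from the trial, it adds that they "should also be reported on the subject Non-Completion of Study Form".

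Section 10.3.1.2 counts by subject. For a repeated AE term, "the event will be counted only once, at the most severe and most-related occurrence". It also tabulates subjects who leave early because of an ADE. Section 10.3.1 keeps every treated subject in the safety set and imputes nothing.

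**The concern.** The subjects whose reactions end their participation are those whose later course a safety study most needs to see. If follow-up may end when participation ends, and the reaction itself may end participation, the plan allows observation to stop in just those subjects. The loss would not be random.

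Two things are at stake. The first is information: Section 7.2 asks for the resolution date, duration and outcome of each event, and 7.3 permits an exit before these are known. A higher grade reached after exit would also be missed, although the safety table is meant to show the worst grade. The second is the subject's protection, since an unresolved reaction would no longer be under observation required by the protocol. Safety is the first objective in the protocol summary, and subjects who leave early because of an ADE are a group that 10.3.1.2 plans to report.

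**Working it through.** The plan gives no figure on this point to reproduce. The check is mainly a comparison of the printed rules.

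1. **Can a reaction cause exit from the study?** Yes. Section 5.3 names a serious reaction. It also names newly met exclusion criteria. In 5.1.2 these include wounds in the target area (criterion 5) and infection, dermatitis or rash in the treatment area (criterion 7). Some of these could be laser reactions, though 5.3 does not say that an expected reaction triggers this route. Section 7.3 itself foresees ADEs, serious or not, that lead to permanent discontinuation from the trial.

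2. **Does exit end required follow-up?** Yes, on the wording of 7.3, which offers end of participation as an alternative to resolution. The section makes no exception for an ADE that is still open and refers to no other section.

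3. **Do the readable safeguards close the gap?**
   - Questioning at each contact (7.2) captures findings up to the last contact. It does not create further contacts.
   - The final evaluation in 5.3 is attempted once, before exit. Its wording ties it to subjects who choose to withdraw; the list of other discontinuation reasons comes afterwards.
   - The Non-Completion form (7.3) records the exit and does not extend follow-up.
   - The SADE report (7.2) does not cover non-serious ADEs and sets no follow-up schedule.
   - The call 3 days after each treatment (4.4.3) is too early to show the outcome of a longer reaction.

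4. **What is kept and what can be lost?** Kept: membership of the safety set, and incidence and severity recorded up to exit. At risk: resolution, duration, outcome and later worsening. If exit comes before the assessment 2 weeks after first treatment, the subject's status for that listed safety endpoint (4.1.1.1) is also unobserved.

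5. **Scale, as illustration.** Inputs: at most 20 subjects (10.1); every treated subject stays in the denominator (10.3.1, 10.3.1.2). Assumption: one subject exits with an open ADE that is a grade worse after exit, or still present at 2 weeks without having been assessed then.
   - Shift in the affected severity category or 2-week count: 1/20 = 5 percentage points.
   - If only 10 subjects were treated (assumption): 1/10 = 10 percentage points.
   - If the ADE does not worsen, the severity table shifts by 0. If it has resolved by 2 weeks, or was assessed then, the 2-week count shifts by 0.

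6. **Total loss.** This cannot be fixed. The visit schedule is partly redacted, and 10.3.1.2 calls the analysis done "when all treated subjects have completed the 12 week post-final treatment visit" an interim one, so later visits may exist.

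**The case against.** The strongest objection is that the text most likely to govern discontinued subjects cannot be read: Section 6 (including 6.4 on follow-up visits), Section 7.1 and Appendix 1. A reader might infer that the plan has no rule for these subjects. The documents do not support that, because a closing rule may stand in the missing parts. What can be said is narrower: 7.3, the section on ADE follow-up, is readable and states its end point without exception.

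The gap also needs several discretionary steps. Retention is the default, discontinuation is permitted and not required, and an investigator would have to discharge someone with an open reaction. This stands and limits how often the gap would occur.

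Three further inferences are tempting but go too far:

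- **That later sequelae of a SADE are excluded because the report is due in 5 working days.** That is a reporting deadline. Section 7.2 does not say that recording closes then, and separately asks for resolution date and outcome.
- **That the exited subject drops out of the safety denominator.** Sections 10.3.1 and 10.3.1.2 keep every treated subject in.
- **That safety results are biased by a known amount.** The 5 points are simply one subject in 20. The study is descriptive with no hypothesis tests, so no decision threshold is affected.

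**Conclusion.** The point holds as a cheap improvement to a stated rule. On the printed text of 5.3 and 7.3, an ADE that causes investigator-initiated discontinuation can go unfollowed while unresolved. The subject then loses required observation, and the safety tables can miss the event's later course, including a worse grade.

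The size is small and conditional: 5 percentage points per affected subject at 20 treated, and 0 if the ADE neither worsens nor persists. It rests on three conditions: that the discontinuation option is used, that the ADE is open at that time, and that no rule in the unreadable sections already keeps such subjects under follow-up. Confidence is medium for that last reason. The planned analysis itself contains no error on this point.

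**What to change.** In 7.3, with a matching line in 5.3, state that a subject discontinued with an open ADE receives no further laser treatment but is followed for that ADE at the post-treatment visits already scheduled, until it resolves or the last scheduled visit is reached, unless consent is withdrawn. In 5.3, apply the final clinical and ADE evaluation to investigator-initiated discontinuations as well as to voluntary withdrawals.

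The cost is a short wording amendment, with the IRB approval that 12.3.1 requires. The downside is that a few subjects attend scheduled visits after treatment has stopped. The proposal uses existing visits, although the redacted schedule prevents a check of exactly which ones apply. If Section 6 or Appendix 1 already contains such a rule, a cross-reference in 7.3 is enough.

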7 ADVERSE DEVICE EFFECTS

7.1. Definitions

Cutera, Inc.

Protocol # C-16-EN12

"A Single-Center, Open-Label Exploratory Study of a Novel Laser for Skin Rejuvenation"

7.2 Recording ADEs and SADEs

All ADEs/SADEs will be: (1) evaluated and must be recorded in the subject's medical chart and in the study case report forms (CRFs); (2) monitored and tracked from the time of the first treatment with the Cutera Enlighten laser system.

At each contact with the subject, the investigator must seek information on ADEs/SADEs by specific questioning and, as appropriate, by examination. ADEs/SADEs may be observed by the investigator and/or clinical research staff, elicited from the subject and/or family member or volunteered by the subject. All observed and volunteered adverse signs and symptoms, anticipated or unanticipated, regardless of severity or frequency, will be recorded in the case histories (medical chart and CRFs). Included in the description should be the nature of the sign or symptom, the date of onset, date of resolution (duration), the severity, anticipated or unanticipated, the relationship to study treatment or other therapy, the action taken (if any), and the outcome.

All SADEs, anticipated or unanticipated, must be reported to Cutera immediately but not later than 5 working days. The SADE must be recorded in: (1) the AE CRF and (2) a written report must be submitted to Cutera within five (5) working days after the investigator first learns of the event and is to include a full description of the event and sequelae, in the format detailed by the Cutera Serious Adverse Device Effect Form.

7.3 Follow-up of Subjects after ADEs and SADEs:

All reported ADEs/SADEs should be followed until resolution or until the subject's participation in the study ends. Resolutions of ADEs/SADEs are to be documented on the appropriate CRFs. All ADEs that result in permanent discontinuation from this clinical trial, whether serious or not, should also be reported on the subject Non-Completion of Study Form.

8 Potential Risks / Benefits

8.1

A 7x4 grid of black bars on a white background. The bars vary in length and position across the grid. The first row has one long bar. The second row has three bars: one long bar on the left, one short bar in the middle, and one long bar on the right. The third row has four bars: one short bar in the top-left, one long bar in the middle-left, one short bar in the middle-right, and one long bar in the bottom-right. The fourth row has four bars: one long bar in the top-left, one short bar in the middle-left, one long bar in the middle-right, and one long bar in the bottom-right. The fifth row has four bars: one long bar in the top-left, one short bar in the middle-left, one long bar in the middle-right, and one short bar in the bottom-right. The sixth row has four bars: one short bar in the top-left, one long bar in the middle-left, one short bar in the middle-right, and one short bar in the bottom-right. The seventh row has four bars: one long bar in the top-left, one short bar in the middle-left, one long bar in the middle-right, and one short bar in the bottom-right.

8.2 Potential Benefits

The subjects may or may not benefit from the treatment with the study device. Potential benefit of laser treatment for photo-rejuvenation is improved appearance of treated area. There is no guarantee of success.

9 Risk Management

The investigator participating in this study was chosen based on extensive and safe experience with the use of lasers in dermatology applications. This is the most critical element in managing subject risk. In addition, study investigators will be trained on the use of the Cutera Enlighten laser system by a representative of Cutera.

10 DATA ANALYSIS PLAN

10.1 Sample Size

Up to 20 subjects will be enrolled in this exploratory study.

